5 STUDY PROCEDURES

This study is a retrospective review of patients who have undergone a carotid endarterectomy procedure with the use of the Sundt™ carotid shunt prior to study initiation.

Eligible subjects for the study should be identified by the 3-digit site number followed by the 3-digit subject ID. Numbering of the subjects should be done in a reverse chronological order with the most recent subject being 001 followed by the second most recent being 002 and so forth.

Required information will be collected through a review of the patient chart or electronic medical records (EMR) by the Principal Investigator or delegated personnel. The delegated staff

member shall collect demographics, details surrounding the procedure, and the post-operative assessment.

- **Demographics**
 - Age
 - Gender
 - Height
 - Weight
 - Relevant Past Medical History
 - Transient Ischemic Attack (TIA)
 - Stroke
 - Asymptomatic Carotid Stenosis
 - Bleeding Disorder
 - Diabetes
 - Smoking
 - Other relevant past medical history per the investigator's opinion
 - Past Surgical History
 - Previous Head or Neck Surgery
 - Previous Head or Neck Radiation
 - Previous Vascular Surgery
 - Other relevant surgical history per the investigator's opinion
 - Diagnosis / Indication for Surgery
 - Medications
- **Procedure**
 - Date of surgery
 - Procedure(s) performed
 - Duration of surgery
 - Device information, including lot number
 - Medications
 - Any complications noted in the operative report and in the investigator's opinion determined to be related to the device
- **Post-operative Assessment (up to 60 days post-procedure)**
 - Evidence of cerebral ischemia as indicated by post-operative neurological exam
 - Evidence of injury to artery as seen on post-operative imaging of the carotid artery either by carotid duplex ultrasound or angiogram

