1.3 Intended Use

The carotid endarterectomy shunts are indicated for temporary carotid artery bypass during carotid endarterectomy procedures in order to help protect the cerebral hemispheres from ischemia during the period of carotid artery occlusion. These shunts are designed as temporary indwelling catheters and are not intended for permanent placement.

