2.2 Primary Study Endpoint

The primary endpoint of this study is evidence of injury to the artery or cerebral ischemia secondary to shunt placement and removal.

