5.1 Device Performance

The delegated site staff will collect information regarding the device performance.

The following device performance questions will be part of the case report form and will be collected from the patient medical record including both the operative note and the anesthesia record for the procedure. For the “yes / no” questions below, if the medical record is silent on the answer to the question it will be assumed that the answer is “no”.

1. Was the shunt use routine or selective? If selective, specify the test and the result that led to use of the shunt.
2. Was there any delay in surgery or complication due to preparation of the device for surgery? If yes, please explain.
3. What was the clamping method type for shunt insertion?
4. How long was the carotid artery cross clamped for shunt insertion?
5. Was there any device-related damage to the artery during insertion of the shunt? If yes, please explain.
6. Was there evidence of clot formation within the shunt at any point during the procedure? If yes, describe how this was detected and what was the remedy. What was the impact to the procedure?
7. Was there any evidence of reduced flow within the shunt other than clot formation (e.g. due to kinking, malposition within the artery)?
8. Was there any evidence of excessive bleeding around the shunt after initial placement? If yes, what was the remedy and the result of that remedy?
9. Did removal of the shunt cause vessel injury or complicate closure? If yes, please explain.
10. Was there evidence of post-operative cerebral ischemia noted in the neurological exam?
11. Did the subject experience injury to the artery due to the device as evidenced by the imaging of the carotid artery either by carotid duplex ultrasound or angiogram?
12. Were there any other device-related complications not previously recorded in the case report forms? If yes, please explain.

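### The primary endpoint puts no source limit on cerebral ischemia, but the items that record it accept only the post-operative neurological exam, so a stroke or TIA charted elsewhere may go uncounted

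*Protocol*

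**What the plan says.** Protocol 2.2 defines the primary endpoint as "evidence of injury to the artery or cerebral ischemia secondary to shunt placement and removal"; SAP 3.1 is the same. Neither names a source of evidence.

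The data items are narrower. The post-operative assessment in Protocol 5 lists "Evidence of cerebral ischemia as indicated by post-operative neurological exam", within a window of up to 60 days. The synopsis and SAP 7.2.6 repeat the item. Question 10 in Protocol 5.1, repeated in SAP 7.2.7, reads "Was there evidence of post-operative cerebral ischemia noted in the neurological exam". No number of exams, timing or examiner is given.

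The sources open to the abstractor are wider than the exam. Protocol 5 sends staff to the patient chart or EMR. Protocol 5.1 says the device performance answers are "collected from the patient medical record including both the operative note and the anesthesia record for the procedure". Under the same section, a yes/no question on which the record is silent is answered no.

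Protocol 6 and SAP 7.1 say that the incidence of arterial injury or ischemia will be summarized. They do not say which case report form items make up that incidence.

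**The concern.** When an endpoint is defined broadly and collected narrowly, an abstractor who follows the form exactly can leave out events that meet the definition. Suppose a patient has a TIA on the ward, recorded in the discharge summary and cleared before an exam was written up. That patient had cerebral ischemia in any ordinary sense, yet the literal answer to question 10 can be no.

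The study is descriptive, so the reported incidence is the main result, and no later analysis step would recover an event that was not collected.

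There is a related gap on the performance side. Protocol 1.3 says the shunt is meant to "help protect the cerebral hemispheres from ischemia during the period of carotid artery occlusion". No item asks directly whether signs of ischemia appeared while the shunt was in place or as it came out, although the anesthesia record is a named source.

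**Working it through.** There is no plan figure to reproduce. The sample size of 100 (Protocol 3.2, SAP 6) comes with no expected rate, precision target or power. The check is a reading of every item that could record ischemia after the shunt went in.

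| Item | Where | Records ischemia as an outcome? | Stated to feed the primary incidence? |
|---|---|---|---|
| Post-operative assessment, ischemia line | Synopsis; Protocol 5; SAP 7.2.6 | Yes, from the neurological exam only | Not stated, but it matches the endpoint |
| Question 10 | Protocol 5.1; SAP 7.2.7 | Yes, from the neurological exam only | Not stated, but it matches the endpoint |
| Question 1 (test that led to selective shunting) | Protocol 5.1; SAP 7.2.7 | No; it records the reason for shunting, not what followed | No |
| Questions 6 and 7 (clot, reduced flow) | Protocol 5.1; SAP 7.2.7 | No; they record shunt flow, and question 6 asks about impact on the procedure | No |
| Operative-report complications | Protocol 5; SAP 7.2.5 | Not labelled ischemia; needs a device-related judgment | No |
| Question 12 (other complications) | Protocol 5.1; SAP 7.2.7 | Not labelled ischemia; needs a device-related judgment | No |
| Adverse event listing | SAP 7.2.8 | Not labelled ischemia; a listing | No |
| TIA and stroke | Protocol 5; SAP 7.2.4 | No; past history only | No |
| Imaging | Protocol 4.1 and 5; SAP 7.2.6 | No; carotid only, read for arterial injury | Arterial injury component only |

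Three steps follow.

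1. The two exam items are the only ones that match the ischemia component, so they are its only identifiable source. This is an inference, because neither document maps the endpoint to the form.
2. Removing valid sources can only remove events. The source restriction taken alone therefore lowers the count or leaves it unchanged. The rule for silent records pushes the same way: an exam that was never charted becomes a no.
3. Question 10 as a whole need not be low. It does not ask for new ischemia, although prior stroke and TIA are expected histories. It also does not ask whether the ischemia was due to the shunt, whereas questions 5, 11 and 12 are tied to the device. An old deficit or an unrelated event within 60 days could be counted.

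The documents give neither a true rate nor the share of events that the exam would catch. The following is illustration only, on assumed values, for clinical events (stroke, TIA or new deficit). With N = 100, true rate *p* and share captured *s*, expected observed events = 100 × *p* × *s*, and the chance of observing none = (1 − *p* × *s*)^100.

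| Assumed *p* | *s* = 100% | *s* = 90% | *s* = 70% | *s* = 50% |
|---|---|---|---|---|
| 2% | 2.0 events; 13% | 1.8; 16% | 1.4; 24% | 1.0; 37% |
| 5% | 5.0 events; 0.6% | 4.5; 1.0% | 3.5; 2.8% | 2.5; 8.0% |
| 10% | 10 events; <0.1% | 9; <0.1% | 7; <0.1% | 5; 0.6% |

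The percentage in each cell is the chance of reporting zero ischemia. For *p* = 2% and *s* = 50%: 100 × 0.02 × 0.5 = 1.0, and 0.99^100 = 0.37. At low rates, incomplete capture makes a report of zero noticeably more likely.

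**The case against.** The strongest reply is that the plan has other routes. The synopsis mentions safety events, Protocol 5 collects device-related complications from the operative report, question 12 is a catch-all, and SAP 7.2.8 lists all adverse events. The endpoint text itself sets no source limit, so a sensible analyst might count a TIA found by any of these routes. That is fair, and it is why the event *may* be left out rather than certainly is. But two of the routes depend on a device-related judgment, none is labelled ischemia, and neither document says that any of them enters the primary incidence.

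Second, nothing limits the patient to one exam. Exams recorded at discharge or readmission within 60 days are eligible, and an exam note may mention a resolved TIA. This stands and reduces the loss. How far depends on local charting.

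Third, the study has no test or threshold, so one or two events change no decision rule. That is true, but the incidence is the result that will be read.

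Four stronger readings are tempting and not supported:

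- *The reported ischemia incidence is biased downward overall.* This holds for the source restriction only. Question 10 can also overcount, as shown above.
- *A definite fraction of events is lost.* No figure in the documents supports one.
- *Intra-operative monitoring changes are lost primary events.* A monitoring change is not by itself clinical ischemia. Questions 5 to 9 already cover insertion, clot, flow, bleeding and removal. What is missing is a performance question.
- *Brain infarcts sit in records already under review.* The operative note and anesthesia record are named, but brain imaging is never mentioned. Its availability will vary by patient and site.

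**Conclusion.** The concern holds in a limited form. The endpoint accepts ischemia from any source, while the items that record it accept only a post-operative neurological exam. A post-operative stroke or TIA charted elsewhere may therefore be missing from the ischemia component even when the form is completed exactly as written.

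The restriction can only lower the count. Its size cannot be derived from the documents, and the net direction of error in question 10 is unknown. The conclusion rests on one inference: that the exam items supply the ischemia component, since no other item is labelled as doing so. If the sponsor intends wider sources, the plan needs to say so. The change is worth making because it closes a gap between the primary endpoint and its measurement at little cost.

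**What to change.** 1. Reword the ischemia item (synopsis, Protocol 5, SAP 7.2.6) and question 10 (Protocol 5.1, SAP 7.2.7) to: *any documented new cerebral ischemia from shunt insertion to day 60: stroke or TIA diagnosis anywhere in the chart, or new deficit on neurological exam*.
2. For each event, record the source and the investigator's judgment of whether it is secondary to shunt placement or removal. Report the incidence overall and by attribution. This also deals with the overcounting risk.
3. Where brain imaging exists, list new infarcts separately by source. Do not merge them into the incidence, because detection would then depend on each site's imaging practice.
4. Add one question after question 7: *Was there a neuromonitoring or awake-exam change suggesting ischemia after shunt placement or at removal? (yes / no / not monitored or not recorded)*. Exempt it from the rule that turns a silent record into a no, and report it on a separate performance line outside the primary incidence.
5. State in Protocol 6 and SAP 7.1 which items make up the primary incidence.

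The cost is a wording change, a few added fields and slightly longer abstraction, mostly from records already opened. The reported incidence may be higher.

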5.1 Device Performance

The delegated site staff will collect information regarding the device performance.

The following device performance questions will be part of the case report form and will be collected from the patient medical record including both the operative note and the anesthesia record for the procedure. For the “yes / no” questions below, if the medical record is silent on the answer to the question it will be assumed that the answer is “no”.

1. Was the shunt use routine or selective? If selective, specify the test and the result that led to use of the shunt.
2. Was there any delay in surgery or complication due to preparation of the device for surgery? If yes, please explain.
3. What was the clamping method type for shunt insertion?
4. How long was the carotid artery cross clamped for shunt insertion?
5. Was there any device-related damage to the artery during insertion of the shunt? If yes, please explain.
6. Was there evidence of clot formation within the shunt at any point during the procedure? If yes, describe how this was detected and what was the remedy. What was the impact to the procedure?
7. Was there any evidence of reduced flow within the shunt other than clot formation (e.g. due to kinking, malposition within the artery)?
8. Was there any evidence of excessive bleeding around the shunt after initial placement? If yes, what was the remedy and the result of that remedy?
9. Did removal of the shunt cause vessel injury or complicate closure? If yes, please explain.
10. Was there evidence of post-operative cerebral ischemia noted in the neurological exam?
11. Did the subject experience injury to the artery due to the device as evidenced by the imaging of the carotid artery either by carotid duplex ultrasound or angiogram?
12. Were there any other device-related complications not previously recorded in the case report forms? If yes, please explain.

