6 STATISTICAL ANALYSIS

The PMCF is a retrospective chart review. All analyses will be descriptive in nature. No formal statistical analyses will be performed. The study objectives will be presented by summary statistics.

Summary statistics (mean, standard deviation, quintiles, counts, and percentages) will be presented for all demographic (i.e. age, gender, etc.), clinical baseline characteristics (diagnosis, medical history, medications), surgical procedures (procedures performed, duration of surgery) and complications.

The primary objective will be evaluated by summarizing the incidence of injury to the artery or cerebral ischemia secondary to shunt placement.

All statistical analysis will be conducted using SAS.

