7.2.1.2. Safety population

The safety population will consist of the patients who undergone a carotid endarterectomy with the Sundt™ carotid shunt. All analysis will be based on the safety population.

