7.2.6. Post-operative Assessment (up to 60 days post-procedure)

Post-operative assessment will be summarized, details will be listed by subject.

- Evidence of cerebral ischemia as indicated by post-operative neurological exam
- Evidence of injury to artery as seen on post-operative imaging of the carotid artery either by carotid duplex ultrasound or angiogram

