7.3. Missing Data

No imputations is planned for missing data. All summaries will be based on the non-missing data.

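### Protocol 5.1 scores a silent chart as no ischemia and no arterial injury, SAP 7.3 uses non-missing data only, and neither document says which fields feed the primary incidence

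*Protocol*

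**What the plan says.** The primary endpoint (Protocol 2.2) is "evidence of injury to the artery or cerebral ischemia secondary to shunt placement and removal". Protocol 6 and SAP 7.1 give the analysis in one sentence: "The primary objective will be evaluated by summarizing the incidence of injury to the artery or cerebral ischemia secondary to shunt placement". That sentence names no source field and no denominator, and it leaves out removal.

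The two components are collected twice.

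- **Device performance items (Protocol 5.1).** Item 10 asks "Was there evidence of post-operative cerebral ischemia noted in the neurological exam". Item 11 asks about device-related arterial injury on duplex ultrasound or angiogram. For the yes/no items, "if the medical record is silent on the answer to the question it will be assumed that the answer is" *no*. SAP 7.2.7 repeats the items but not this rule.
- **Post-operative assessment, up to 60 days (Protocol 5, SAP 7.2.6).** One field is "Evidence of cerebral ischemia as indicated by post-operative neurological exam", and a matching field covers arterial injury on imaging. No rule for silent records is stated here. The SAP says only: "Post-operative assessment will be summarized, details will be listed by subject".

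Protocol 4.1 requires post-operative imaging records but sets no time window for them, and it does not require a neurological exam. The only exclusion (Protocol 4.2) is shunt insertion at an infected site. SAP 7.2.1.2 defines the safety population by endarterectomy with the shunt and adds: "All analysis will be based on the safety population". SAP 7.3 plans no imputation: "All summaries will be based on the non-missing data".

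**The concern.** In a chart review, silence about an intraoperative event in an operative note is some evidence that nothing happened. Silence about a neurological exam may mean only that no exam was done or filed. Protocol 5.1 treats the two alike. Because the rule acts at data entry, item 10 reaches the analysis with nothing missing, and the non-missing rule in SAP 7.3 has nothing to act on. A patient never examined then looks the same, on that item, as one examined and found normal.

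The study is descriptive, so the incidence is its whole primary result. The plan does not require the report to show how many patients were assessed for either component. The two sets of fields can also give different rates from the same charts.

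**Working it through.** The documents contain no figure to reproduce. The sample size of 100 has no stated derivation, and no event rate or rate of undocumented exams is given. The check is therefore a comparison of the rules, followed by an illustration with assumed inputs.

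**1. The same patient under each route.** Take an eligible patient with imaging on file and no neurological exam on file.

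| | Item 10 (Protocol 5.1) | Assessment field (Protocol 5, SAP 7.2.6) |
|---|---|---|
| Value when the record is silent | *no* | no rule stated; blank if left empty |
| Effect of SAP 7.3 | none, nothing is missing | patient leaves the ischemia summary |
| Contribution | in the denominator, event-free | not in the denominator |
| Stated link to the primary incidence | none | none |

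Imaging has a similar gap. A patient whose only imaging falls after day 60 meets the entry criterion but has no imaging within the assessment window.

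**2. Ischemia alone, in counts.** Assume x = 3 recorded ischemia events in 100 patients, with s silent charts. Item 10 gives x/100 = 3.0% whatever s is. The non-missing rule gives x/(100 − s): 3/90 = 3.3% at s = 10 and 3/70 = 4.3% at s = 30. The ratio 100/(100 − s) is 1.11 and 1.43.

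**3. Composite if silent means *no*.** Assume a true composite of 5%, made up of i (imaging-detected) and q (ischemia-only) without overlap. Imaging is complete, a fraction s of exams is silent, and r is the ischemia risk in silent relative to documented charts. The reported composite is

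L = i + (1 − s)·q / [(1 − s) + s·r].

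- i = q = 2.5%, r = 1: s = 0.1 gives 2.5 + 0.9 × 2.5 = 4.75%; s = 0.3 gives 2.5 + 0.7 × 2.5 = 4.25%. The shift is 0.25 and 0.75 points.
- q = 1.25%, r = 1: 4.88% and 4.63%. q = 3.75%, r = 1: 4.63% and 3.88%.
- i = q = 2.5%, r = 2: 2.5 + 0.9 × 2.5/1.1 = 4.55%, and 2.5 + 0.7 × 2.5/1.3 = 3.85%.
- i = q = 2.5%, r = 0 (no ischemia in silent charts): 5.0% in both cases, so no shift.

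In this model L never exceeds 5%. The ischemia component (true 2.5%, r = 1) is reported as 2.25% and 1.75% under silent = *no*, and as 2.5% among those examined.

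**4. Undetermined patients counted as events.** These are patients with a silent exam and negative imaging, a fraction s(1 − i). With i = q = 2.5% and r = 1, the figures are 4.75 + 0.1 × 97.5 = 14.5% and 4.25 + 0.3 × 97.5 = 33.5%. In counts, 3 composite events with 10 or 30 undetermined patients of 100 gives 3% to 13% or 3% to 33%.

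**5. Composite among determined patients only.** This keeps imaging-positive patients without an exam and drops imaging-negative ones: L / [(1 − s) + s·i]. The results are 4.75/0.9025 = 5.26% and 4.25/0.7075 = 6.01%. It overstates the assumed 5% even though silence is unrelated to risk.

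**The case against.** The strongest reply is that the endpoint wording matches the post-operative assessment fields, which carry no silence rule, while the 5.1 items sit under a device performance heading and are summarized separately. On that reading SAP 7.3 governs and 5.1 does not touch the primary incidence. This stands as the more natural reading, but no sentence states it. A reader might infer that the primary incidence is certainly biased downward. The documents do not support that: the effect on it is conditional. What holds without condition is the effect on the summaries of items 10 and 11.

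A second reply is that the listings would reveal silent charts. Item 10 alone cannot, since a stored *no* is the same either way. Read together, a blank assessment field and a *no* on item 10 might separate them. That depends on the CRF, which is not in the documents, and the plan does not ask for the comparison.

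A third is that the imaging criterion protects item 11. It does so only in part, because it has no time window.

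A fourth is that the endpoint is worded as evidence, so that silence may fairly count as none, and that the rule is openly prespecified in a study with no test or threshold. This is a possible definition, but the rate then cannot be interpreted without the number assessed.

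Finally, the shift is small. In the base case it is under one patient per 100, and at an assumed 2% composite it would be 0.1 to 0.3 patients. The exact 95% interval for 5/100 is 1.6% to 11.3%. This stands, and it limits the weight of the point.

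**Conclusion.** The point holds in a limited form. As written, the plan records patients without the relevant assessment as event-free on items 10 and 11. Relative to full ascertainment in the same patients, those summaries can be lowered or left unchanged, never raised. The primary incidence shares this direction only if those items feed it. If the assessment fields feed it, SAP 7.3 drops such patients instead. The choice is not stated, and 5.1 and 7.3 are not reconciled.

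The base-case shift of 0.25 to 0.75 points rests wholly on assumed inputs: a 5% composite, half ischemia-only, complete imaging, and 10% to 30% silent exams unrelated to risk. It disappears if silent charts hold no ischemia and reaches 1.15 points (5.0 − 3.85) at 30% silence with doubled risk.

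A reader might take 14.5% or 33.5% as plausible rates or as a firm ceiling. They are neither. They need every undetermined patient to be an event, and they leave out silence on items 5 and 9 (arterial damage at insertion, vessel injury at removal), which match the endpoint's reference to placement and removal and might contribute to it. This should be fixed, but it does not invalidate the study.

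**What to change.** 1. In Protocol 6 and SAP 7.1, name the fields that feed each primary component; the post-operative assessment fields match the endpoint wording. Say whether items 5 and 9 contribute. Keep the attribution to both shunt placement and removal, which item 10 does not carry.
2. For items 10 and 11, replace silent = *no* with three options: yes, no (assessment documented), not documented. Use the same options in the matching assessment fields, and reconcile Protocol 5.1 with SAP 7.3.
3. Report the number with a documented neurological exam and the number with documented imaging within 60 days. Give each component's incidence among those assessed, noting that it is off if silence is related to risk.
4. Report the composite over all patients with *not documented* counted as no event, labelled a lower bound. Beside it, give a sensitivity figure counting undetermined patients as events. State that this is an exception to SAP 7.3 and that it does not cover silence on items 5 or 9 if they contribute. Do not lead with a determined-only composite (working, step 5).

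The cost is one extra response option on four fields, unless the CRF already records whether the exam was done, plus a few lines of text. A component denominator may fall below 100, and the sensitivity range will be wide if many exams are undocumented.

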1.2 Study Device

1.2.1 Device Description

The Integra Sundt™ internal and external (Loop) Carotid Endarterectomy Shunts are designed to provide temporary carotid bypass for cerebral circulation during carotid endarterectomy procedures.

The Sundt™ internal and external Carotid Endarterectomy shunts are constructed of silicone elastomer with stainless steel spring reinforcement to minimize kinking and occlusion of the cannula lumen and to aid in the ease of insertion of the proximal and distal ends. The ends of the shunts have cone-shaped bulbs to facilitate fixation of the shunt in the vessel. Quite frequently in the internal type shunt a distal tourniquet is not required because, if the proper shunt size is selected, the bulb fits firmly enough against the wall of the vessel that there is no bleeding around the distal bulb. A tourniquet is always required on the proximal end of both the external and internal shunts and usually on the distal end of the external shunt

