3.1. Primary Study Endpoint

The primary endpoint of this study is evidence of injury to the artery or cerebral ischemia secondary to shunt placement and removal.

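### The primary endpoint and question 9 attribute arterial injury to placing or removing the shunt, but questions 5 and 11 ask only about injury caused by the device, so the placement count can fall short of the endpoint

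*Protocol*

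**What the plan says.** Protocol 2.2 defines the primary endpoint as "evidence of injury to the artery or cerebral ischemia secondary to shunt placement and removal", and SAP 3.1 repeats it. The cause named is an act: putting the shunt in and taking it out.

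The items that could record arterial injury use three different terms:

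- **Removal.** Question 9 in Protocol 5.1 follows the endpoint: "Did removal of the shunt cause vessel injury or complicate closure".
- **Placement.** Question 5 asks "Was there any device-related damage to the artery during insertion of the shunt".
- **Imaging, with attribution.** Question 11 asks "Did the subject experience injury to the artery due to the device as evidenced by the imaging of the carotid artery".
- **Operative complications.** Protocol 5 and SAP 7.2.5 collect "Any complications noted in the operative report and in the investigator's opinion determined to be related to the device". Question 12, the catch-all, is also limited to device-related complications.
- **Imaging, without attribution.** The post-operative assessment in Protocol 5 and SAP 7.2.6 records "Evidence of injury to artery as seen on post-operative imaging of the carotid artery either by carotid duplex ultrasound or angiogram", within 60 days.

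SAP 7.2.7 repeats the twelve questions. Neither document defines device-related or says which items make up the primary endpoint.

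**The concern.** Placement and removal are two parts of one endpoint, yet the form asks about them on different causal terms. An injury caused by taking the shunt out is a yes to question 9 whatever its mechanism. An injury caused by putting it in is a yes to question 5 only if someone also judges it device-related.

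The difference could affect foreseeable events. Inserting and holding the shunt involves manipulation and fixation of the vessel. Protocol 1.2.1 says "A tourniquet is always required on the proximal end of both the external and internal shunts", and questions 3 and 4 record clamping for insertion. If the operator damages the artery while inserting the shunt, the site may reasonably see a fault of technique rather than of the device.

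At stake is whether the study's only primary result measures the endpoint as written. In a single-arm safety review of 100 subjects, a few events decide how the injury rate reads.

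**Working it through.** The documents state no injury rate, precision target, alpha or power, so there is no plan figure to reproduce. The check is mainly a comparison of wording.

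**Step 1. Attribution by item**

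| Item | Cause required |
|---|---|
| Endpoint (Protocol 2.2, SAP 3.1) | Placement and removal of the shunt |
| Question 9, removal | Removal of the shunt |
| Question 5, insertion | Device |
| Question 11, imaging | Device |
| Question 12, other complications | Device |
| Operative-complications field (Protocol 5, SAP 7.2.5) | Device, in the investigator's opinion |
| Post-operative imaging (Protocol 5, SAP 7.2.6) | None |

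**Step 2. Follow one case.** The operator tears the artery while inserting the shunt, repairs it, and ascribes it to technique. Under the endpoint it is secondary to placement. Question 5, question 12 and the operative-complications field can each be answered no, because each requires device-relatedness. Question 11 requires it too. The unqualified imaging item remains, but a repaired tear may not be visible there. The same tear made during removal is a yes to question 9.

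**Step 3. The silent-record rule.** Protocol 5.1 sets a yes/no answer to no when the record does not address the question. The rule concerns silence, not attribution. Even so, a note that describes a tear without a view on device-relatedness could be read as silent on question 5.

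**Step 4. Scale at N = 100** (Protocol 3.2, SAP 6). Exact (Clopper-Pearson) 95% limits for x events: lower = 2.5th percentile of Beta(x, 100 − x + 1); upper = 97.5th percentile of Beta(x + 1, 100 − x). The lower limit is 0 when x = 0.

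| Events | Incidence | Exact 95% CI |
|---|---|---|
| 0 | 0% | 0–3.62% |
| 1 | 1% | 0.03–5.45% |
| 2 | 2% | 0.24–7.04% |

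**Step 5. Illustration with assumed inputs, none from the documents.** Let p be the true placement-injury rate and s the share classed as not device-related and not picked up elsewhere. Expected count = 100 × p × (1 − s). Chance of counting none = (1 − p(1 − s))^100.

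| p | s | Expected count | Chance of counting none |
|---|---|---|---|
| 2% | 0 | 2.0 | 0.98^100 = 13% |
| 2% | 25% | 1.5 | 0.985^100 = 22% |
| 2% | 50% | 1.0 | 0.99^100 = 37% |
| 5% | 0 | 5.0 | 0.95^100 = 0.6% |
| 5% | 25% | 3.75 | 0.9625^100 = 2.2% |
| 5% | 50% | 2.5 | 0.975^100 = 8.0% |

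These rows show only how sensitive a small count is. They do not estimate the loss in this study.

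**The case against.** The strongest reply is that the wording differs but no harm is shown. Several parts of it stand.

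- **Device-related is undefined.** Question 5 already names insertion, so an abstractor could count any damage done while inserting the shunt. A reader might infer that technique injuries *are* scored no. The documents support only that they *can* be.
- **The endpoint's source items are not named.** The unqualified imaging item echoes the endpoint's wording, and inclusion criterion 3 requires imaging records for every subject. If that item feeds the incidence, injury from the endarterectomy itself might be counted, which would push the rate up. A reader might infer a one-way downward bias in the primary result; without an item mapping, its direction is not established.
- **Other traces exist.** Question 8 asks about bleeding around the shunt without a device limit, the procedures performed might show a repair, the synopsis mentions safety events, and SAP 7.2.8 promises a listing of all adverse events. None is a dedicated arterial-injury field, and Protocol 5 and 5.1 contain no unqualified adverse-event field to supply that listing.
- **Clamp injury is ambiguous.** Protocol 1.1 treats clamping as part of the endarterectomy, so such an injury need not be secondary to the shunt. The endpoint text does not settle the matter for clamp or tourniquet.
- **A device limit is defensible** where the objective is the shunt's safety and efficacy. If that is the intention, the endpoint should say so, and question 9 should match.

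The reply does not remove the mismatch between question 5 and question 9, or the lack of any dedicated field free of the device limit for a placement injury found and repaired at operation.

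**Conclusion.** The point holds as a mismatch between the endpoint and the items that collect it. Placement injury is asked about on a narrower cause than the endpoint states, and removal injury is not. Measured against the endpoint, the device limit in question 5 can only leave placement injuries out, so that count can fall short. Whether the reported primary incidence does so depends on two things the documents leave open: how sites read device-related, and which items are counted.

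The size is unknown. One event is one percentage point at 100 subjects, so one or two reclassified injuries would visibly change the result. The study is descriptive and sets no threshold, so no formal decision turns on this. What is affected is whether the reported rate means what the endpoint says. That merits correction and goes beyond tidying, since the item wording governs what the primary result can count.

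**What to change.** 1. Reword question 5 to match question 9: *Did placement of the shunt cause vessel injury? If yes, please explain.*
2. Reword question 11 to ask for injury to the artery secondary to shunt placement or removal, as shown on imaging.
3. Add a separate field for each injury: *device-related: yes / no / cannot be determined*.
4. State in SAP 7.1 and 7.2.7 that the injury part of the primary incidence counts any subject with an injury secondary to placement or removal from questions 5, 9 or 11, each subject once, and that the device-related subset is reported beside it.
5. State whether clamp or tourniquet injury counts as secondary to placement. This is for the sponsor to decide.
6. Carry the wording through Protocol 5.1 and SAP 7.2.7, and restore removal to the analysis sentences in Protocol 6 and SAP 7.1, which mention placement only.

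The cost is two reworded questions and one extra field, completed from records already under review. The injury rate may come out slightly less favourable. Nothing is lost, because the device-related count stays available.
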